**Table 5 LLOQ for Different Assay Versions**

Influenza Type	Assay Version	LLOQ (log 10 vp/ml)
Influenza A	Version 1 50µl, 2014	2.18
	Version 1 20µl, 2019	2.48
	Version 2 20µl, 2023	2.79
Influenza B	Version 1 50µl, 2014	2.93
	Version 1 20µl, 2019	2.63

Patients with a positive by RT-PCR on Day 1 will be included in this analysis.

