### **Time to Cessation of Viral Shedding by RT-PCR**

Time to cessation of viral shedding by RT-PCR, in hours, is defined as the time between the initiation of study treatment and first time when the virus RNA by RT-PCR qualitative result is negative (no cycle threshold [Ct]-value detectable). Patients who do not have a negative result by the last observation time point will be treated as censored at that time point. For the patients with multiple virus types, this endpoint is defined as the time between the initiation of the study treatment and first time when the virus RNA by RT-PCR qualitative result is negative for all virus types. One day is converted into 24 hours.

Patients with a positive qualitative result on Day 1 will be included in this analysis.

This endpoint will be summarized using descriptive statistics, as well as Kaplan-Meier plots.

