### **Change from Baseline in the Amount of Virus RNA (RT-PCR) at Each Timepoint**

Change from baseline in the amount of virus RNA (unit:  $\log_{10}$  vp/mL) will be presented and is defined as the change from baseline in the amount of virus RNA on Days 2, 4, 6, and 10.

If the amount of virus RNA is less than the lower limit of quantification, the amount of virus RNA will be imputed as the relevant LLOQ ( $\log_{10}$  vp/mL). If a patient is infected with multiple virus types, the sum of virus RNA ( $\log_{10}$  vp/mL) will be used for analysis.

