### **Area under the Curve in the Amount of Virus RNA (RT-PCR)**

Area under the concentration–time curve (AUC) in virus RNA (RT-PCR) will be presented and is defined as AUC of change from baseline in the amount of virus RNA (RT-PCR). AUC is calculated using the trapezoidal method similar to AUC in virus titer. Patients with a positive RT-PCR result on Day 1 will be subjected to this analysis. The lower limit of quantification is defined as 2.18 for flu A and 2.93 for flu B (log10 vp/mL). If a patient is infected with multiple virus types, the sum of those the amount of virus RNA will be used for analysis.

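### RNA change from baseline (and RNA AUC, if the same imputation applies) admits infants whose baseline is RT-PCR positive but unquantifiable; with one virus type and one assay version they cannot show a decline

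*SAP*

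**What the plan says.** All of the rules are in SAP 4.3.2.

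- **Entry, RNA change from baseline** (sentence after Table 5): "Patients with a positive by RT-PCR on Day 1 will be included in this analysis".
- **Entry, RNA AUC:** "Patients with a positive RT-PCR result on Day 1 will be subjected to this analysis". This AUC is itself defined on change from baseline.
- **RT-PCR status:** for time to cessation of shedding, the event is the first time the "qualitative result is negative (no cycle threshold [Ct]-value detectable". The proportion-positive endpoint likewise counts positive qualitative results. No quantitative definition of RT-PCR positivity is given.
- **Imputation:** below the quantification limit, "the amount of virus RNA will be imputed as the relevant LLOQ". Baseline is not excepted, and a negative sample has no separate value.
- **Limits:** Table 5 gives 2.18, 2.48 and 2.79 log10 vp/mL for three influenza A assay versions, and 2.93 and 2.63 for two influenza B versions. The RNA AUC subsection has its own line: "The lower limit of quantification is defined as 2.18 for flu A and 2.93 for flu B".
- **Titer, for comparison:** the titer AUC subsection sets the limits of quantification and detection both at 0.75 log10 TCID50/mL, and lower titers are imputed as 0.749 in the change-from-baseline subsection.

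**The concern.** Entry depends on a qualitative result, while the outcome is a quantity with a floor. Between no detectable Ct and the LLOQ lies a zone where an infant counts as positive but has no measurable amount. An infant whose baseline falls there starts on the floor, so no fall can be recorded even if the virus clears completely. The zero comes from the imputation and says nothing about the drug.

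Low baselines are plausible. Protocol 4.1.1 allows entry up to 96 hours after symptom onset, and the qualifying influenza test may precede screening by up to 48 hours. SAP 4.5.1 plans a listing of influenza-infected patients who are RT-PCR negative at baseline, so the plan foresees even undetectable baseline samples.

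At stake are two descriptive secondary virology summaries. With about 30 infants, one or two structural zeros would be visible in a mean.

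**Working it through.** The plan states no expected result for these endpoints, so there is no figure to reproduce. The check applies its rules to one affected infant.

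**Inputs.** Imputation: y below L becomes L, where L is the applicable LLOQ. Swabs on Days 1, 2, 4, 6 and 10 give t = 0, 1, 3, 5, 9 days. The baseline-adjusted trapezoid from the titer AUC subsection, to which the RNA AUC subsection refers, is the sum over k of (y_k + y_(k-1) - 2y_0)(t_k - t_(k-1))/2.

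**Case 1: positive but below L at baseline, negative afterwards, one virus type, one assay version.**
- Every value becomes L, so the change at each visit is L - L = 0.00.
- Each AUC term is (L + L - 2L)(t_k - t_(k-1))/2 = 0, so the AUC of change is 0.00.
- This holds for all five Table 5 limits and for the two limits in the RNA AUC subsection.

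**Case 2: same baseline, Day 2 RNA at L + 0.5, then below L.**
- Day 2 change is +0.50; later changes are 0.
- AUC of change = 0.5 x 1/2 + 0.5 x 2/2 = 0.25 + 0.50 = +0.75 log10 x day.
- A rise is recorded in full, but a fall cannot be recorded.

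**Titer comparison.** The limits of quantification and detection are both 0.75, so titer has no detected-but-unquantifiable zone.

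**Effect on a mean.** If k of N infants contribute a structural zero and the other N - k average m, the reported mean is m(N - k)/N, a shrinkage of k/N. For illustration, take N = 30 (the planned enrollment) and m = -1.75 log10, the Day 2 RNA change in the earlier Japanese pediatric study (Protocol 1.2.4). Using both here is an assumption.
- k = 0: -1.75
- k = 1: -1.75 x 29/30 = -1.69
- k = 3: -1.75 x 27/30 = -1.58
- k = 5: -1.75 x 25/30 = -1.46

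The documents do not give k.

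**Where the identity fails.** If one infant's samples were run on different assay versions, the imputed values would differ: 2.48 - 2.18 = 0.30, 2.79 - 2.48 = 0.31 and 2.79 - 2.18 = 0.61 for influenza A; 2.93 - 2.63 = 0.30 for B. The spurious change would then be 0.30 to 0.61 log10 in size instead of 0. With more than one virus type the amounts are summed, so one type below its limit does not floor the total.

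**The case against.** The case against acting has real weight.

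- **Little depends on these endpoints.** The study has one arm and no hypothesis test, and the endpoints are secondary and descriptive. Added zeros understate the mean decline, which is the cautious direction. This stands.
- **Clearance is still captured.** Time to RT-PCR negativity and the proportion RT-PCR positive use the qualitative result. This also stands, and it is why the defect is confined to the two quantity endpoints.
- **Requiring a quantifiable baseline selects on higher baselines.** It moves the mean decline away from zero, and infants just above the LLOQ remain partly floored. This is fair, and is the reason to show both sets.
- **Two steps are inferred.** The two entry rules say positive without adding qualitative; that meaning comes from the neighboring endpoints. The RNA AUC subsection gives limits but does not restate the imputation. The first inference is well supported because no other definition exists. The second is reasonable, but the AUC part remains conditional on it.

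A reader might size the problem by the chance that a baseline falls below the LLOQ. With assumed normal baselines and limits of 2.18 to 2.93, that chance runs from about 0.2-0.9% (mean 6.5, SD 1.5) to about 12-22% (mean 4.5, SD 2). The documents do not support these as estimates. They give no baseline distribution and no RNA limit of detection, and the tail includes infants with no detectable Ct, whom the entry rule already excludes. Under each assumed distribution the figure is only an upper bound.

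**Conclusion.** The concern holds within limits. RNA change from baseline admits infants with a detectable but unquantifiable Day 1 sample and, for a single virus type on one assay version, gives them a change that is 0 on clearance and never negative. The same is true of the RNA AUC of change if the LLOQ imputation applies there.

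The direction is certain: each structural zero shrinks a mean decline by 1/N. The overall size is unknown because the number of such infants is not given and may be zero. The illustrated shift from -1.75 to -1.69 or -1.58 rests on 30 analyzed infants and a borrowed mean.

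A reader might infer that the change is floored at zero whatever happens. The documents do not support that for mixed infections or for samples run on different assay versions. Nor do they support a claim that the trial's view of viral clearance is compromised, since the qualitative endpoints are unaffected. This is a gap in two descriptive summaries that should be closed because closing it is easy.

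**What to change.** In SAP 4.3.2, for RNA change from baseline and RNA AUC:

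1. Require Day 1 baseline RNA at or above the LLOQ of the assay version used.
2. Report the number of infants who are RT-PCR positive but below the LLOQ at baseline, and list them.
3. Keep them in the proportion-positive and time-to-negative RT-PCR analyses.
4. Show the full RT-PCR-positive set as a sensitivity analysis. The reverse arrangement is also acceptable, provided the number below the LLOQ at baseline is reported.
5. State whether the LLOQ imputation applies to the RNA AUC. At the same time, reconcile that subsection's limits of 2.18 and 2.93 with Table 5, where they match only the 2014 rows.

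This takes a few sentences of SAP wording and no new data. The cost is that a few infants may leave two descriptive summaries. That matters slightly where numbers are small: Cohorts II and III have minimums of 4 and 3. Infants just above the LLOQ stay partly floored, since the largest fall they can show is their baseline minus the LLOQ.

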#### **Proportion of Patients with Positive Influenza Virus Titer at Each Timepoint**

Proportion of patients positive for influenza virus titer will be presented at each visit and is defined as the percentage of patients whose influenza virus titer is not less than the lower limit of quantification (0.75 log10TCID50/mL) or positive among those assessed for influenza virus titer on Days 2, 4, 6, and 10.

Patients with a positive influenza virus titer on Day 1 will be included in this analysis.

#### **Proportion of Patients Positive by RT-PCR at Each Timepoint**

Proportion of patients positive by RT-PCR will be presented at each visit and is defined as the percentage of patients with a positive qualitative result among those assessed by RT-PCR on Days 2, 4, 6, and 10.

Patients with a positive RT-PCR result on Day 1 will be included in this analysis.

#### **Area under the Curve in Virus Titer**

Area under the concentration–time curve (AUC) in virus titer will be presented and will be calculated using the trapezoidal method. AUC change from time 0 (t0) to time K (tK) is given by the formula:

$$\sum_{k=1}^K \frac{(y_k + y_{k-1})(t_k - t_{k-1})}{2}$$

where tk (hours) represents the date of the kth viral titer assessment (k=0, ..., K) and yk represents the log10 value of the kth viral titer assessment (TCID50/mL).

Twenty-four hours of time will be converted into one day. Patients with a positive virus titer on Day 1 will be included in this analysis. The lower limit of quantification and lower limit of detection is defined as 0.75 log10TCID50/mL for flu A and 0.75 log10TCID50/mL for flu B. If a patient is infected with multiple virus types, the sum of those virus titers will be used for analysis.

Additionally, the AUC in virus titer adjusted for baseline will be presented and will be calculated using the trapezoidal method. AUC of change from baseline from time 0 ( $t_0$ ) to time K ( $t_K$ ) is given by the formula

$$\sum_{k=1}^K \frac{(y_k + y_{k-1} - 2y_0)(t_k - t_{k-1})}{2}$$

where  $t_k$  (hours) represents the date of the  $k^{\text{th}}$  viral titer assessment ( $k = 0, \dots, K$ ) and  $y_k$  represents the  $\log_{10}$  value of the  $k^{\text{th}}$  viral titer assessment (TCID50/mL).

Twenty-four hours will be converted into one day. Patients with a positive virus titer on Day 1 will be subjected to this analysis. The lower limit is defined as 0.75 log10TCID50/mL for flu A and 0.75 log10TCID50/mL for flu B. If a patient is infected with multiple virus types, the sum of virus titers (TCID50/mL) will be used for analysis.

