## **2. STATISTICAL HYPOTHESES AND SAMPLE SIZE DETERMINATION**

### **2.1 STATISTICAL HYPOTHESES**

The primary objective of this study is to evaluate the safety of baloxavir marboxil in pediatric patients from birth to <1 year with influenza-like symptoms. Therefore, and as it is a single group study, there will be no formal statistical hypothesis testing.

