**Table 2 Acceptable Time Windows for Parameters other than Data from the Patient Diary and PK Assessments**

Time Point (Scheduled Time point)	Acceptable Time Window
Pre-dose at Visit 1 (Day 1) a	Before dosing on Day 1
Post-dose at Visit 1 (Day 1) a	After dosing on Day 1
Visit 2 (Day 2)	Day 2
Optional Visit 1 (Day 3)	Day 3
Visit 3 (Day 4)	Between Day 4 and Day 5
Visit 4 (Day 6)	Between Day 6 and Day 7
Visit 5 (Day 10)	Between Day 8 and Day 12 as follows: If a patient presents between Day 8 and Day 11 and presents on Day 12 then the visit between Day 8 and Day 11 will be classed as Visit 5 and the Day 12 visit will be classed as Optional Visit 2 If a patient does not present between Day 8 and Day 11 and presents on Day 12 this will be classed as Visit 5
Optional Visit 2 (Day 15)	Between Day 12 and Day 22
Visit 6 (Day 29)	On or after Day 23

a If time is missing for data collected on Visit 1 where this data should be collected at 'v1 screening' or 'v1 post-dose' as per the schedule of activities, then it is defined as 'Pre-dose at Visit 1 (Day 1)' or 'Post-dose at Visit 1 (Day 1)', respectively.

Measurements collected within the acceptable time window for each scheduled assessment time point, including data obtained at the time of withdrawal, will be used for the analyses of all endpoints at each assessment time point. For all patients with multiple values within a visit window, the value obtained closest to the target time point will be used. If two measurements collected with the same time deviation exist before and after the target time point, the measurement obtained before the target time point will be adopted for analysis. The assessment time point having no measurements within the corresponding acceptable time window will be considered as missing.

In the assessment of data from sources other than the patient diary, if there are multiple values which may be adopted for a scheduled assessment time point (even though the above rules have been strictly followed), the measurements at the time point entered in the Case Report Form (CRF) will be adopted.

For summaries of data not collected by visit, such as AEs, medical history and concomitant medications, all data up to the study completion/discontinuation date will be included.

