**Table 6 PB1 and PB2 Gene Sequencing**

Criteria	
1) Subjects who exhibit viral titer rebound:	
Viral titer at [(a certain time point) – (just before time point)] <math>\geq 2 \times SD</math> value of viral titer of control virus in assay a.
 
a Viroclinics database;
 
Influenza A - control virus data generated from 09 May 2017 until 30 November 2022 – Lot#: VC-170180018:
 
 
A/PR/8/1934: <math>3.82 + 0.36 \log_{10} \text{TCID50/mL}</math> (mean +/- SD) (<math>n = 521</math>); <math>2 \times SD = 0.72</math>
 
 
control virus data generated from 26 July 2022 until 04 May 2023 - Lot#: VC-220180034:
 
 
A/PR/8/1934: <math>2.19 + 0.49 \log_{10} \text{TCID50/mL}</math> (mean +/- SD) (<math>n = 90</math>); <math>2 \times SD = 0.98</math>
 
 
Mean SD of both lots to be used, therefore <math>2 \times SD = 2 \times ((0.36 + 0.49) / 2) = 0.85</math>
 
Influenza B - control virus data generated from 09 May 2017 until 04 May 2023:
 
 
B/Lee/1940: <math>5.33 + 0.45 \log_{10} \text{TCID50/mL}</math> (mean +/- SD) (<math>n = 516</math>); <math>2 \times SD = 0.90</math>
 

2) Subjects who continue to shed virus at Day 6 and beyond:	Viral titer ( $\log_{10}$ TCID50/mL) at Day 6 and beyond $>1.5$
3) Subjects who do not show a reduction in virus titer:	Viral titer ( $\log_{10}$ TCID50/mL) at a certain time point: A $>1.5$ Viral titer ( $\log_{10}$ TCID50/mL) at just before time point: B $>1.5$ AND Viral titer ( $\log_{10}$ TCID50/mL) at ([a certain time point: A]–[just before time point: B]) $\geq 0$

SD=standard deviation; TCID50=50% tissue culture infectious dose.

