## Appendix 2 Schedule of Activities (cont.)

- i Perform if the investigator determines that influenza symptoms are persisting or at the investigator's discretion.
- j Record vital sign measurements if abnormal physical examination, adverse events recorded since last visit, or at investigator's discretion on Day 29.
- k At least two nasopharyngeal swabs (one for each nostril) will be taken at each visit.
- l PK samples (all patients): See [Appendix 3](#) for collection timepoints for baloxavir marboxil and S-033447 concentration samples. Patients will be assigned to have either the Day 2 or the Day 4 sample. Only one sample from Days 6 to 10 is required and can be collected at either Visit 4 or Visit 5.
- m The palatability assessment should be completed by the study investigator (or delegate) who administers baloxavir marboxil to the patient.

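### The viral AUCs in SAP 4.3.2 have no stated end day and are not normalised for length, and the RNA AUC fixes quantification limits that contradict SAP Table 5

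*SAP*

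**What the plan says.** **End of the AUC.** SAP 4.3.2, *Area under the Curve in Virus Titer*, gives two trapezoid sums from t_0 to t_K, one unadjusted and one of change from baseline, where t_k "represents the date of the kth viral titer assessment (k=0, ..., K"). K is not tied to a day or visit. The 24-hour sentence only converts units. The RNA AUC is an AUC of change from baseline, calculated in a similar way. Inclusion requires only a positive Day 1 result.

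**Neighbouring endpoints.** These do name days. For RNA, change from baseline is "the change from baseline in the amount of virus RNA on Days 2, 4, 6, and 10"; titer change and both proportion-positive endpoints use the same four days. The AUC paragraphs do not repeat them.

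**Timing of swabs.** SAP Table 2 accepts Visit 5 "Between Day 8 and Day 12 as follows", and has later windows for Optional Visit 2 (Days 12 to 22) and Visit 6 (Day 23 onward). The schedule marks the Day 15 and Day 29 swabs as optional: "Perform if the investigator determines that influenza symptoms are persisting", or at the investigator's discretion.

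**RNA limit.** For change from baseline, values below the limit take the relevant LLOQ from the table "LLOQ for Different Assay Versions": flu A 2.18, 2.48 or 2.79; flu B 2.93 or 2.63 log10 vp/mL. The RNA AUC paragraph says: "The lower limit of quantification is defined as 2.18 for flu A and 2.93 for flu B".

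**The concern.** An AUC of change from baseline that is not divided by its length grows more negative with every day spent below baseline. Two infants with the same viral course can therefore score differently because one was swabbed for longer. Three sources of unequal length are possible:

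- a last swab before Visit 5;
- the five-day window for Visit 5, if t_k is the actual date;
- the optional late swabs, if they are counted. These are taken mainly when symptoms persist, so they would lengthen the AUC in slow recoverers and make them look better.

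The RNA limit is a different defect. Two current paragraphs can give the same below-limit sample two different values, so the RNA AUC and the RNA change from baseline would not rest on the same data.

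At stake are the accuracy and reproducibility of a listed secondary virology endpoint in about 30 infants, where a few atypical records show in the mean.

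**Working it through.** The plan states no AUC value, so there is none to reproduce. All viral profiles below are assumed.

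**Inputs.** Swabs on Days 1, 2, 4, 6 and 10, so t = 0, 1, 3, 5, 9 days. A titer below the limit is set to 0.749; the SAP states this for change from baseline, and it is assumed here for the AUC. Assumed baseline 5 log10.

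- Fast clearer: 5, 2, then 0.749. Changes: 0, -3, -4.251, -4.251, -4.251.
- Slow clearer: 5, 4, 3, 2, 0.749. Changes: 0, -1, -2, -3, -4.251.

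**Adjusted titer AUC**, sum of (d_k + d_(k-1))(t_k - t_(k-1))/2 with d = y - y_0:

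- Fast, to Day 10: -1.500 - 7.251 - 8.502 - 17.004 = -34.26. Stopping at Day 6: -17.25. Stopping at Day 4: -8.75.
- Slow, to Day 10: -0.5 - 3 - 5 - 14.502 = -23.00. Adding a Day 15 swab: -23.00 - 5 × 4.251 = -44.26.

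**Visit 5 window**, same Visit 5 value on a different date. The unadjusted AUC is the adjusted AUC plus 5 × t_K.

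| | Day 8 | Day 10 | Day 12 | Shift from Day 10 |
|---|---|---|---|---|
| Fast, adjusted | -25.8 | -34.3 | -42.8 | 8.50/34.26 = 24.8% |
| Slow, adjusted | -15.8 | -23.0 | -30.3 | 7.25/23.00 = 31.5% |
| Fast, unadjusted | 9.2 | 10.7 | 12.2 | 1.50/10.74 = 13.9% |
| Slow, unadjusted | 19.2 | 22.0 | 24.7 | 2.75/22.00 = 12.5% |

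**Effect on a mean of 30** (assumed 15 fast, 15 slow). All ending on Day 10: (-34.26 - 23.00)/2 = -28.63.

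- In these profiles the AUC is linear in the Visit 5 date, with slopes 4.251 (fast) and 3.626 (slow) per day. Half on Day 8 and half on Day 12 therefore gives -28.63 again.
- If the date is equally likely to be any of Days 8 to 12, its SD is √2 = 1.414 days. The SD of the mean is √[15(1.414 × 4.251)² + 15(1.414 × 3.626)²]/30 ≈ 1.02, and 1.02/28.63 is just under 4%.
- Three fast infants stopping at Day 4: 3 × (34.26 - 8.75)/30 = 2.6 smaller in size (9%).
- Three slow infants with a counted Day 15 swab: 3 × 21.26/30 = 2.1 larger in size (7%).

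**Second profile as a check.** Protocol 1.2.4 reports a mean titer change of -4.20 on Day 2 in an earlier pediatric study. Holding that drop, the AUC is -2.1 - 4.2(t_K - 1): -10.5 (last swab Day 4), -27.3, -35.7 and -44.1 (Visit 5 on Day 8, 10 and 12), and -56.7 (Day 15 counted). The window shift is 8.4/35.7 = 23.5% each way.

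**RNA limit.** Assumed profile 7, 5, 4, L, L, where L is the imputed limit. AUC = -1 - 5 + (L - 10) + 4(L - 7) = 5L - 44.

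| | AUC paragraph limit | Table 5 limit | Difference |
|---|---|---|---|
| Flu A, 2023 assay | L = 2.18: -33.10 | L = 2.79: -30.05 | 5 × 0.61 = 3.05 |
| Flu B, 2019 assay | L = 2.93: -29.35 | L = 2.63: -30.85 | 5 × 0.30 = 1.50 |

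The error runs in opposite directions for the two virus types. The fixed limits are the values of the 2014 assay rows in Table 5.

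**The case against.** **Day 10 is probably meant.** The adjusted titer AUC and the RNA AUC are AUCs of change from baseline, and that change is defined on Days 2, 4, 6 and 10. A reader might infer that Day 15 and Day 29 swabs do enter the AUC. The documents do not support that: the AUC text neither includes nor excludes them. The Table 6 criterion "Subjects who continue to shed virus at Day 6 and beyond" selects samples for sequencing and says nothing about AUC scope. This objection largely stands; what remains is that the end day is unstated.

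**The Visit 5 effect may not arise.** Table 2 assigns measurements to scheduled time points, so nominal days are a possible reading, and under them the effect vanishes. The word date in the formula favours actual timing but does not settle it. A reader might also infer that the window moves the reported mean by about a quarter. That requires every infant to deviate in the same direction.

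**Early last swabs are covered.** A reader might infer that there is no rule. Read literally there is one: the sum stops at the last assessment, which truncates. The fault is its effect on the adjusted AUC.

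**The unadjusted titer AUC is a partial safeguard.** It moves about half as much across the Visit 5 window and keeps fast and slow clearers in order.

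**Little depends on it.** The SAP says "there will be no formal statistical hypothesis testing", AUC is not among the virology subgroup analyses, and clearance is shown by other endpoints. This stands and limits the weight of the point. It does not remove the conflict over the RNA limit.

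**Conclusion.** The point holds in limited form. The AUC text leaves the end day open and, taken literally, makes the baseline-adjusted titer AUC and the RNA AUC depend on length of swabbing. The clearest case is truncation: -8.8 instead of -34.3 for an assumed fast clearer last swabbed on Day 4. The Visit 5 window matters for individual values (about 25 to 32%) but little for the mean (about 4% SD under symmetric timing), and only if actual dates are used. Inflation from late swabs (-44.3 against -23.0 for the slow clearer) is conditional on a reading that the neighbouring endpoints argue against.

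The RNA limit is a plain contradiction in current text, worth about 3.1 log10·days for flu A on the 2023 assay and 1.5 for flu B on the 2019 assay in the assumed profile.

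All sizes rest on assumed profiles. The documents do not give the frequency of early or late last swabs, or how many samples were run on each assay version. No test, sample size or decision rule is affected.

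**What to change.** 1. In the RNA AUC paragraph, replace the fixed limits with the assay-version LLOQs of Table 5, as already used for change from baseline in RNA.
2. Define all viral AUCs from Day 1 to Day 10 (Visit 5) at nominal visit days: 0, 24, 72, 120 and 216 hours. State that optional Day 15 and Day 29 swabs do not enter the AUC and stay in time to cessation and the listings.
3. Report how many infants have no Visit 5 swab, and show the AUC summary with and without them.

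The cost is a few SAP sentences and minor programming, with no new data. The downside is that nominal days ignore small true differences in timing.
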